5.1 Eligibility criteria

Eligible adult patients (≥ 18 years old) were identified and recruited at the participating trial site centres starting in August 2018 and ending by June 2022, 52 patients will be recruited. Participating trial centres will include the Liver and Metabolic Units at the Humanitas Gradenigo Hospital (Turin) since August 2018), and the Metabolic Unit of Dept of Medical Sciences at the Città della Salute e della Scienza hospital (Turin) since Sept 2018).

All trial participants will give informed written consent at the beginning of the screening visit prior to undergoing any tests and procedures needed to assess eligibility.

Eligibility for the trial will be determined at screening visit 1 by standard blood tests, clinical history (including written-confirmation of drug history where necessary) and physical examination to identify other illnesses or contraindications for participation.

Patients who satisfied the eligibility criteria trial at both sites will be offered to take part in a metabolic mechanistic substudy. The substudy involves a standard Oral Glucose tolerance Test (OGTT) and a standard Oral Fat Tolerance Test (OFTT) on three admissions (at least 24 hours apart from each other) and an indirect calorimetry test at the two participating centres on visits 2 (pretreatment) and 8 (4 weeks

post-treatment). A detailed summary of the metabolic substudy will be published separately. A patient's decision to partake or withdraw from the metabolic substudy will not affect their participation in the main 72-week trial.

A schematic view of trial schedule and design is presented in **Figure 1**.

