5.5 Randomization, stratification and blinding

Randomization and stratification

Participants meeting all the eligibility criteria and providing written informed consent will be randomized centrally on a 1:1 basis to either of the two-study treatments (phytosomal curcumin vs placebo) using computer generated randomization. To ensure even distribution between groups in key baseline covariates, randomization will be stratified into blocks of 4 according to the following variables: diabetes status (present vs. absent), obesity status (present vs. absent), fibrosis stage (stage F3-4 vs. stage 0-2), CKD (present vs. absent). Trial participants will be allocated a unique trial identification number to preserve patient confidentiality and enable the study to be double-blinded. Patients, investigators, assessors, trial site staff, and the sponsor (except for specific laboratory staff and individuals responsible for safety) remained blinded to treatment assignment throughout the trial.

Medication preparation and blinding/unblinding procedures

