-Improvement in anthropometry, physical activity and dietary parameters (body weight, BMI, waist circumference), physical activity and daily dietary consumption.

-Improvement in glycaemic control (fasting plasma glucose, HbA1c)

-Improvement in cardiovascular risk profile: fasting plasma lipids, oxidative stress markers, inflammatory markers/adipokines and chemokine MCP-1.

-Chronic kidney disease (CKD) regression. CKD will be defined according to Kidney Disease Improving Global Outcomes (KDIGO) guidelines as sustained (i.e., documented on 2 occasions at least 3 months apart) reduction in estimated Glomerular Filtration Rate [eGFR] <60 mL/min/1.73 m² **and/or** sustained increase in albumin excretion rate (AER) ≥30 mg/d. CKD regression will be defined as sustained (i.e., documented 3 month apart, on both follow-up visit 7 and visit 8) estimated Glomerular Filtration Rate [eGFR] ≥60 mL/min/1.73 m² **and** normalization of AER (i.e., <30 mg/d).

eGFR will be assessed from serum creatinine using the **CKD-EPI** (Chronic Kidney Disease Epidemiology Collaboration) equation, as recommended by KDIGO guidelines⁴². eGFR and AER will be classified according to KDIGO categories⁴³

-Change in absolute values of eGFR^{44, Error! Bookmark not defined.}, and of albumin excretion rate(AER).

We will estimate mean annual rates of change in eGFR from baseline to the final follow-up visit (total slopes), within each treatment allocation using linear mixed model repeated measures (MMRM);

adjustments were made for age, baseline eGFR, baseline urinary AER, diabetes, baseline fibrosis stage, systolic blood pressure, angiotensin-converting enzyme/angiotensin receptor blocker⁴⁵(see. **supplementary material**)

Exploratory outcomes

We explored the effect of treatment on Nuclear Factor(NF)-kB activation in the liver and in circulating mononuclear cell(MNCs). NF-kB is a key proinflammatory transcription factor involved in NASH development and progression and a known molecular target of curcumin (see Methods and supplementary material).

Safety outcomes

Safety end points include adverse events after the start of treatment, biochemical assessments, and clinical assessments. Selected events (including deaths, cardiovascular events, and acute pancreatitis) were adjudicated by an independent, external event-adjudication committee, whose members were unaware of the treatment assignments. A complete list of the trial end points is provided in protocol Table 1.

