The pro-inflammatory transcription factor **Nuclear Factor(NF)- κ B** is a master regulator at the crossroads of metabolic, oxidative, immune and inflammatory pathways and a known molecular target of curcumin(3,49). NF- κ B activation in all liver cell subtypes and in peripheral mononuclear cells (MNCs) plays a central role in NASH pathogenesis and progression and in NAFLD-associated metabolic abnormalities((⁵⁰, ⁵¹, ⁵²,⁵³, ⁵⁴). We therefore assessed the effect of treatment on NF- κ B activation in the liver and in circulating MNCs.

Nuclear Factor(NF)- κ B activation in the liver by immunohistochemistry

The ImmunoCruz® Staining System will be used in deparaffinized liver tissue according to the manufacturer's instructions (Santa Cruz Biotechnology, Santa Cruz, CA). Briefly, slides will be soaked in 3% hydrogen peroxide for 5 min, washed, and incubated in serum blocking solution for 20 min. Specimens will be then incubated with primary antibodies for 2 h at 37° C. Tissue samples will be probed with mouse monoclonal antibodies reactive to NF- κ B p65 (Santa Cruz Biotechnology). After rinsing, specimens will be incubated with biotinylated secondary antibody and a horseradish peroxidase-streptavidin complex, for 30 min each. Tissue samples will be then colorized with DAB substrate, counterstained, mounted, and examined. NF- κ B immunoreactivity will be expressed as the % of positive cells/high-power field ($\times 400$)⁵⁵ and will also be semiquantitatively evaluated using a 4-point scoring system (0—no staining; 1—positive staining in <30% of cells/high-power field; 2— positive staining in 30–70% of cells/high-power field; 3—positive staining in >70% of cells/high-power field).

NF- κ B activation in circulating mononuclear cells(MNCs).

Blood samples were collected in tubes containing Na-EDTA as an anticoagulant; 3.5 mL of the anticoagulated blood sample was carefully layered over 3.5 mL of the PMNL isolation medium (Robbins Scientific Corp, Sunnyvale, CA). Samples were centrifuged at 450 x g in a swing outrotor for 30 min at 22 °C. At the end of centrifugation, 2 bands separate out at the top of the red blood cell pellet. The top band consists of mononuclear leukocytes(MNCs), whereas the bottom band consists of polymorphonuclear leukocytes(PMNs). The MNC and PMN bands were harvested with a Pasteur pipette, repeatedly washed

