We estimated mean annual rates of change in eGFR from baseline to the final follow-up visit (total slopes), by treatment allocation using linear mixed model repeated measures (MMRM); adjustments were made for age, sex, first baseline CKD stage, baseline eGFR; baseline urinary ACR, diabetes, history of cardiovascular disease, systolic blood pressure, angiotensin-converting enzyme/angiotensin receptor blocker use⁷⁹

Proteinuria will be estimated using measurements of urinary protein and creatinine at baseline and at baseline and at each visit thereafter.

Albuminuria and eGFR stage will be categorized according to the KDIGO classification system⁸⁰

The end-stage renal disease was defined as kidney transplantation or the receipt of dialysis for at least 30 days unless death occurred.

For exploratory outcomes, we will explore the existence of a threshold in hepatic NF-kB activation change predicting histological response (NASH resolution, fibrosis improvement) using the area under receiver operating characteristic curve (AUROC) analysis and Youden index.

A sensitivity analysis will be performed in which missing data were handled by reference-based multiple imputation informed by data from placebo recipients (see **Preplanned subgroup and sensitivity analyses suhealing**).

Safety will be analysed descriptively

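### The exploratory search for a hepatic NF-kB threshold names no treatment term and no correction for choosing the cut, so accuracy at the cut will look too good and, if arms are pooled, allocation alone can produce apparent prediction

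*Protocol*

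**What the plan says.** Section 9.2 of the protocol sets one analysis linking the liver marker to outcome. It will "explore the existence of a threshold in hepatic NF-kB activation change predicting histological response", where response means NASH resolution or fibrosis improvement, "using the area under receiver operating characteristic curve (AUROC) analysis and Youden index". The sentence mentions no treatment arm, covariate or internal validation.

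The immunohistochemistry text in section 8.1.2 puts the marker on two scales. It "will be expressed as the % of positive cells/high-power field", and it "will also be semiquantitatively evaluated using a 4-point scoring system".

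Section 7 (Exploratory outcomes) lists a separate randomised question: "We explored the effect of treatment on Nuclear Factor(NF)-kB activation in the liver" and in circulating mononuclear cells. It calls NF-kB "a known molecular target of curcumin".

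On size, section 5.1 says "52 patients will be recruited" and section 5.5 says patients are "randomized centrally on a 1:1 basis".

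**The concern.** Two separate problems can arise.

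**Optimism.** The Youden cut is the one that looks best in the data at hand. Judging it on those same patients overstates how well it separates responders from non-responders, and in a sample this small the overstatement is large.

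**Allocation as a common cause.** The protocol expects curcumin to act on NF-kB and to raise response. If both happen and the two arms are put into one ROC curve, patients with larger NF-kB falls will more often be responders because more of them took curcumin. That would appear even if NF-kB change and response were unrelated among patients on the same treatment.

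At stake is how a published threshold would be read: as a sign that NF-kB reduction tracks healing in the individual patient, with accuracy figures that others might try to apply.

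**Working it through.** The protocol gives no figure for this analysis, so there is none to reproduce. It also gives no variance or expected treatment effect for NF-kB, so the marker shifts below are assumptions and are shown as a range.

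**Inputs from the protocol**
- 52 patients allocated 1:1 gives 26 per arm. With the 10% dropout of section 9.1, 26 × 0.9 = 23.4, so I take 23 biopsied per arm.
- Planning rates in section 9.1: 15% with lifestyle intervention and 20 to 50% with curcumin. These refer to surrogate markers. I also use 38%, the stated success rule (8/21 = 0.381).
- Expected responders: 23 × 0.15 = 3.5 on placebo, plus 23 × 0.20 = 4.6, 23 × 0.38 = 8.7 or 23 × 0.50 = 11.5 on curcumin. The total is about 8, 12 or 15.

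**Assumptions.** The marker is the NF-kB reduction in SD units, normally distributed. Allocation shifts it by d = 0.5, 1.0 or 1.5 SD. The true responder difference within arm is 0 or 0.8 SD.

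**1. Optimism at the chosen cut.** I simulated 23 per arm, with arms pooled and no treatment shift, chose the cut by maximum J = sensitivity + specificity − 1, then applied it to new patients.

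| Response rates | True difference | Apparent J | J in new data |
|---|---|---|---|
| 15% vs 20% | 0 | 0.22 | 0.00 |
| 15% vs 38% | 0 | 0.19 | 0.00 |
| 15% vs 50% | 0 | 0.18 | 0.00 |
| 15% vs 50% | 0.8 SD | 0.43 | 0.28 |

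In the last row, apparent sensitivity and specificity are 0.73 and 0.70, against 0.62 and 0.66 in new data.

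The mean AUROC in the same runs was 0.50 when there was no association. With the 0.8 SD difference it was 0.71, which matches its true value Φ(0.8/√2) = 0.714. So the AUROC is not inflated by choosing the cut.

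Searching for the cut within each arm does not help. With 23 patients and no association, mean apparent J is 0.33 at 15% response and 0.23 to 0.24 at 38 to 50%.

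**2. Allocation alone, if arms are pooled.** Let a and b be the curcumin share among responders and non-responders. With no link within arm,

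pooled AUROC = 0.5 + (a − b)(Φ(d/√2) − 0.5).

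For 15% vs 50%:
- a = 0.50/0.65 = 0.769
- b = 0.50/1.35 = 0.370
- a − b = 0.399

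For 15% vs 38%, a − b = 0.717 − 0.422 = 0.295. For 15% vs 20%, a − b = 0.571 − 0.485 = 0.087. Φ(d/√2) is 0.638, 0.760 and 0.856 for the three shifts.

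| Response rates | d = 0.5 | d = 1.0 | d = 1.5 |
|---|---|---|---|
| 15% vs 50% | 0.56 | 0.60 | 0.64 |
| 15% vs 38% | 0.54 | 0.58 | 0.60 |
| 15% vs 20% | 0.51 | 0.52 | 0.53 |

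Simulation at 21 per arm agrees for 15% vs 50%: 0.56, 0.61 and 0.65. There the unadjusted rank test, which is the test of the AUROC, was significant at two-sided 0.05 in 8%, 19% and 35% of trials. With treatment accounted for, the AUROC returned to 0.50 and the error rate to about 5%.

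**The case against.** **Pooling is not stated.** Section 9.2 is silent on whether arms are pooled, and a statistical analysis plan that is not shown could settle it. This stands: the allocation result is conditional on pooling. It does not remove the point, because the cut is optimistic either way, and more so by arm at placebo-like response rates.

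**Power.** A reader might infer that cutting a continuous marker costs power. The AUROC uses the full ranking and does not lose it. At 21 per arm and a 0.8 SD difference, the rank test has 62% power and a median split 34%, but the plan contains no median split. Nor does it name a significance test at the Youden cut, so false-positive rates for such a test describe something that is not planned.

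**Dependence on assumptions.** The protocol gives no expected NF-kB shift, and at the low end of its response range the allocation effect is negligible (0.51 to 0.53). This also stands.

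**Weight.** It is tempting to say that the trial's mechanistic evidence fails. The documents do not support that. The treatment effect on NF-kB in liver and mononuclear cells is a separate randomised comparison, and there is a metabolic substudy. The threshold search is already labelled exploratory, and ROC with Youden is a usual tool for exploring a threshold.

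**Conclusion.** The point holds in a limited form. The protocol fixes a method that chooses and judges a cut on the same patients, at most 52, without correction. Under the stated assumptions J at that cut is overstated by about 0.15 (0.43 against 0.28) when the marker is truly predictive, and by about 0.18 to 0.22 when it is not.

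If arms are pooled, an AUROC of up to about 0.65 can come from allocation alone at 15% vs 50% response, with much less at smaller response differences. That any threshold found would merely reflect allocation goes further than the text allows: it needs pooling, a treatment shift in the marker and a response difference together, with no association within arm.

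Severity is minor. The analysis is exploratory and feeds neither the primary test nor the 8-of-21 rule. It is a cheap improvement.

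**What to change.** Keep the exploratory ROC aim and add two provisions to section 9.2.

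1. Make the main association analysis a penalised or exact logistic model of response on the continuous change in percentage of NF-kB-positive cells, with treatment arm as a covariate and baseline NF-kB if the number of responders allows. Report the odds ratio per SD with its 95% CI. Alternatively, report an AUROC stratified by arm. Either choice also settles how the arms are handled.
2. If a Youden cut is shown, give bootstrap optimism-corrected sensitivity and specificity, repeating the choice of cut in every resample, and call the cut hypothesis-generating.

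The cost is a few lines of text and code, with no new data or visits. The downside is that reported accuracy will be lower, and with about 8 to 15 responders the adjusted estimate will be imprecise.

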9.3 Methods in analysis to handle missing data

The primary imputation method for missing data will be the non-responder imputation for primary and secondary dichotomous outcomes. This approach does not rely on an assumption of missing at random and is considered conservative for estimating the treatment effect.

To investigate the sensitivity of the histological results with regard to the handling of missing

data, post-hoc sensitivity analyses using multiple imputation will be conducted. These analyses are based on the same CMH method as for the main analyses but using a multiple imputation at random method for missing data(see following Subheading)

9.5 Prespecified additional subgroup and sensitivity analyses

As previously specified, the primary imputation method for missing data will be the non-responder imputation for primary and secondary dichotomous outcomes.

To investigate the sensitivity of the results of the primary analysis with regard to the handling of missing data, a sensitivity analysis using imputation based on unconditional reference was performed for the primary and secondary outcomes. The analysis is based on the same type of non-parametric method as for the primary analysis but with missing data handled by a method of multiple imputation which assumes that the unobserved outcomes are well described by the observed outcomes of the subjects in the placebo arm with similar baseline characteristics. The imputation is done by random sampling of observed outcomes from placebo subjects with the same baseline diabetes status, obesity status, fibrosis stage and CKD status. Multiple (100) replicates of a complete data set will be generated and, for each complete data set, the log risk ratios will be estimated together with the asymptotic standard errors. The estimates and standard errors for the 100 complete data sets were pooled using Rubin's rule to obtain a single estimate of the risk ratio and a 95% confidence interval. The analysis differs from the primary analysis in that it assumes that subjects with missing week 72 data had the same chances of NASH resolution as subjects with week 72 data in the placebo group. If there will be more missing week 72 data in the phytosomal curcumin group than in the placebo group, this analysis would be less conservative than the primary analysis and probably give a better estimate of the treatment effect. The handling of missing data is analogous to the "copy reference" approach for longitudinal normal data presented by Carpenter et al.⁸¹

We also plan to perform the following subgroup analyses to assess the effect of the following characteristics on main efficacy and safety outcomes:

-trial site

-diabetes status, obesity status, CKD status, fibrosis stage (F3-4 vs F0-2)

-per protocol analysis (only patients who completed treatment, had EOT liver biopsy and no major protocol deviations will be included).

All analyses will be carried out with Easy R ver1.61, Saitama, Japan⁸².

10. Ethics and Dissemination

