Preliminary human data indicate curcumin supplementation improves surrogate markers of liver disease and of metabolic risk in NAFLD patients^{20, 21}. The combination of curcumin with phospholipids greatly improves oral bioavailability of curcumin, allowing greater systemic concentrations and delivery to target organs^{22, 23}, and curcumin-phosphatidylcholine phytosome complex administration for up to 18 months was well-tolerated, safe²⁴ and improved clinical end-points and inflammatory parameters in patients with osteoarthritis, uveitis and chronic kidney disease (CKD)^{25, 26, 27}.

2. Research Hypothesis and Aims

On the basis of above-mentioned data, we hypothesized that treatment with phytosomal curcumin would result in significant improvement in liver histology in patients with NASH.

Key secondary hypotheses include tolerability and safety of phytosomal curcumin and the potential to improve NASH-related CKD, systemic inflammation, glucose and lipid metabolism.

To test this hypothesis, we designed a phase II, multicentre, double-blinded, placebo-controlled randomized controlled trial (RCT).

3. Study Design setting and timeline

This is a 72-week, investigator-initiated, multicentre, randomized, double-blinded, placebo-controlled trial of treatment with phytosomal curcumin 1 g daily for adults with biopsy-proven NASH. Screening was undertaken within 14 days of randomisation to assess eligibility and collect baseline data. Patients who satisfied the eligibility criteria were randomly assigned (1:1) to receive oral phytosomal curcumin 1 g daily (experimental) or placebo (control). After which, a 12-week washout period is scheduled.

The trial will be conducted at two University hospitals (HUMANITAS Gradenigo, Turin, Italy, and Città della Salute e della Scienza, Turin, Italy) between May 25th, 2018 and Dec 30th, 2022.

The primary outcome measure will be assessed using an intention-to-treat analysis of the proportion of evaluable patients achieving an improvement in liver histology between liver biopsies at baseline (within 6 months of screening) and after 72 weeks of treatment. Histological improvement will be defined as a

combination of resolution of active steatohepatitis and no worsening in fibrosis (assessed by Kleiner Fibrosis score²⁸; detailed in outcome section).

4. Ethics and regulatory approval

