9.2 Methods for analysis of primary and secondary outcomes

All evaluable patients will be analysed on an intention-to-treat basis. Evaluable patients are defined as those who have had an end-of-treatment biopsy, irrespective of the amount of treatment they have received.

Patients will be categorised as either achieving the primary histological endpoint (ie, NASH resolution) or not. The proportion of patients with a reported improvement in liver histology will be presented and compared across treatments descriptively with 95% CIs.

The primary analysis will be based on a Cochran–Mantel–Haenszel test based on all randomised patients for the in-trial period with missing data handled as non-responders. The common risk ratio between phytosomal curcumin and placebo was estimated along with exact 95% CI. To test for superiority, the exact two-sided p-value was calculated as the sum of probabilities of outcomes having equal or lower probability than the observed outcome under the null hypothesis.

Adjustments for multiplicity testing in the primary analysis will be performed with the use of the Benjamini-Hochberg procedure; each active-treatment group was compared with the placebo group. Two-sided P values <0.05 were considered statistically significant.

An unpowered, preplanned secondary analysis of categorical outcome measures will be done using the χ^2 test or Fisher exact test, as appropriate, of the difference between the proportions of patients with histological improvement in each treatment group.

A preplanned logistic regression analysis will be undertaken to determine the treatment effect when adjusted for the stratification variables (diabetes status, obesity status, fibrosis stage, CKD status) and trial site. We will calculate adjusted relative risks using the Mantel-Haenszel test. Two-sided P values <0.05 will be considered statistically significant in all analyses.

Continuous secondary outcome measures will be compared between treatment groups using linear

regression, adjusting for parameter baseline values and allocated treatment (as model covariates, equivalent to ANCOVA), with multilevel modelling for key continuous outcome measures to account for repeated measures within each patient.

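### The rule that P<0.05 is significant in all analyses also covers the five-factor efficacy subgroups, so chance subgroup results in 52 patients would count as significant

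*Protocol*

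**What the plan says.** Three statements in the protocol bear on this.

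- **Subgroups (Section 9.5).** "We also plan to perform the following subgroup analyses to assess the effect of the following characteristics on main efficacy and safety outcomes". The list gives trial site, diabetes, obesity, CKD and fibrosis stage split at F3-4 against F0-2. Section 3 states "The trial will be conducted at two University hospitals", so site also has two levels. The per-protocol analysis appears as a further item in the same list.
- **Significance (Section 9.2).** "Two-sided P values <0.05 will be considered statistically significant in all analyses".
- **Multiplicity (Section 9.2).** "Adjustments for multiplicity testing in the primary analysis will be performed with the use of the Benjamini-Hochberg procedure". No other part of the plan has a multiplicity rule.

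The protocol does qualify other analyses. The NF-kB outcomes are called exploratory (Sections 7 and 9.2), and the chi-square/Fisher comparison of proportions is called unpowered (Section 9.2). The subgroup analyses carry neither label and stand under a heading that calls them prespecified. Section 9.2 also says that safety will be described rather than tested.

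**The concern.** Read together, these statements give any subgroup P value below 0.05 the standing of a prespecified, statistically significant result. With five factors there are ten levels in which a treatment difference can reach that threshold by chance, in a trial of 52 patients. A trial with no effect could then report significant efficacy confined to, say, patients with diabetes, CKD or F3-4 fibrosis. A significant result in one level and a non-significant one in the other would not show that the effect differs between them. The defect lies in a rule that the protocol states. A later analysis plan that called the subgroups exploratory would have to contradict Section 9.2 to do so.

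**Working it through.** The protocol states no error rate for the subgroup analyses, so there is no figure of its own to reproduce. The size has to be derived.

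**Inputs from the protocol**
- 52 patients (Section 5.1), allocated 1:1 (Section 5.5): 26 per arm.
- Five two-level factors (Sections 3 and 9.5): 5 × 2 = 10 levels. With even splits, 52/2 = 26 patients per level, or 13 per arm.
- Threshold: two-sided 0.05 (Section 9.2).
- Tests: for categorical outcomes, chi-square "test or Fisher exact test, as appropriate"; for the primary outcome, "the exact two-sided p-value was calculated as the sum of probabilities of outcomes".
- Response rate: 15% with lifestyle intervention (Section 9.1).

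**Assumptions, where the protocol is silent**
- Each level is tested separately.
- Factor prevalences are 50% throughout, or between 30% and 60%. Correlation between factors is 0 or 0.4.
- Null response rates of 30% and 50% are taken beside the stated 15%.

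**Bounds under independence**
- 5 tests: 1 − 0.95^5 = 22.6%
- 10 tests: 1 − 0.95^10 = 40.1%

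The ten level-wise tests are not independent, because every patient belongs to five levels, and tests on small counts do not use the full 0.05. Null trials were therefore simulated, 4,000 per scenario. The Monte Carlo standard error near 30% is √(0.3 × 0.7 / 4000) ≈ 0.7 percentage points.

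**Chance of at least one P<0.05 among the ten levels, one outcome, no treatment effect**

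| Response rate | Fisher | Chi-square, uncorrected | Chi-square, continuity-corrected |
|---|---|---|---|
| 15% | 10–12% | 21–26% | 5% |
| 30% | 16–18% | 30–32% | 10–11% |
| 50% | 18% | 30–32% | 12% |

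A continuous outcome compared by t-test gives 29–31%. A separate simulation with 50:50 factors and response rates of 15–50% gave 11–20% (Fisher) and 26–33% (uncorrected chi-square). Taken together, the ranges are about 10–20%, 21–33% and 5–12% for the three tests.

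**Which test applies.** Expected responders per arm in an evenly split level are 13 × 0.15 = 1.95, 13 × 0.30 = 3.9 and 13 × 0.50 = 6.5. The first two are below the customary 5, so Fisher is the natural choice at 15% and 30%. Choosing Fisher whenever an expected count is below 5, and uncorrected chi-square otherwise, gives 10% at a 15% response rate and 18–20% at 30%.

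**Null overall result with a significant level.** The share of all null trials in which the overall comparison is not significant but at least one level is: 10–16% (Fisher), 20–27% (uncorrected chi-square), 24–26% (t-test).

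**Interaction tests instead.** Five treatment-by-factor tests, each at 0.05, give at least one significant result in about 5–19% of null trials for a binary outcome and 21–23% for a continuous one. At 0.01 per factor the continuous figure falls to about 5%. Changing the test without changing the significance rule therefore does not remove the problem.

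**The case against.** **The missing interaction test.** A reader might infer that its absence is itself the error. The documents do not support that. Section 9.5 lists factors and names no method, and the choice between an interaction term and a display by level is commonly left to a statistical analysis plan, which is not at hand. Section 9.2 does say "A preplanned logistic regression analysis will be undertaken to determine the treatment effect when adjusted for the stratification variables", but that model serves adjustment and says nothing about how subgroups will be handled. Nor is the missing term the main cause of the inflation, as the interaction figures show. This objection stands.

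**Testing by level.** The protocol does not say that each level will be tested. The wording in Section 9.5 could be read as a prognostic question or as effect modification. This also stands, so the percentages are conditional. The blanket threshold, however, applies under either form of testing.

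**Scope of the sentence.** The P<0.05 sentence closes a paragraph on adjusted models in a section on primary and secondary outcomes, so it may not have been meant for Section 9.5. But Section 9.2 has already set the 0.05 threshold once, directly after the multiplicity sentence. The second statement extends it to all analyses, and its plain words take in the subgroups.

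**Mitigation.** The list is short and prespecified, and four of its five factors are the randomisation strata (Section 5.5). The trial's decisions rest on the overall Cochran–Mantel–Haenszel test and the rule of 8 responders out of 21, not on a subgroup. This limits the harm to reporting and interpretation. It does not remove it.

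**Conclusion.** The point holds as a defect in a stated rule: Section 9.2 grants significance at 0.05 to every analysis, and Section 9.5 adds five-factor efficacy subgroups without an exemption or an exploratory label. For one binary outcome, if each level is tested, the chance of a false significant subgroup is about 10–20% with Fisher, 21–33% with uncorrected chi-square and 5–12% with continuity correction. This rests on 26 patients per arm, assumed factor prevalences and correlations, and null response rates of 15–50%.

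Three stronger readings are not supported:

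- That the risk is always at least 15%. At the protocol's own 15% response rate with Fisher it is 10–12%, and with continuity correction about 5%, which is nominal.
- That safety outcomes multiply the error. Section 9.5 mentions them, but Section 9.2 makes safety descriptive, so no safety P values are planned.
- That listing the per-protocol analysis among the subgroups distorts a result. That population is selected after randomisation and is not a baseline characteristic, but the section heading also covers sensitivity analyses, and the placement changes no calculation.

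**What to change.** - **Section 9.2:** limit the P<0.05 sentence to the primary and secondary comparisons in all randomised patients.
- **Section 9.5:** state that, for each of the five baseline factors, the treatment-by-factor interaction is estimated on the primary outcome. Report the treatment effect and 95% CI in each level, make no significance claim within a level, and label all subgroup results exploratory.
- **Editorial:** list the per-protocol analysis separately, as a supportive sensitivity analysis.

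The cost is a few sentences and a small change to the subgroup output. The primary analysis, sample size and trial conduct are untouched. The downside is that no significance claim can be made inside a subgroup.
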